## 12.4 PERIODIC MONITORING VISITS

Monitoring visits will be conducted in accordance with Guidance for Industry, Oversight of Clinical Investigations – A Risk-Based Approach to Monitoring, August 2013, and the study-specific monitoring plan. The monitor should visit each site at an appropriate frequency to ensure the following:

- Facilities continue to be adequate and acceptable.
- The protocol is being properly followed.
- The IRB has approved or been notified of any protocol changes.
- Accurate, complete, and current records are being maintained, and the information recorded and submitted to the Sponsor is representative of the subject's records and other supporting documentation.
- Accurate, complete, and timely adverse event reports are being submitted to the Sponsor.
- Informed consent has been obtained.
- The reason for a subject's withdrawal from the study has been documented.
- Reports are being submitted to the IRB and Sponsor.
- The appropriate staff is conducting study activities.

The investigator or designee must, upon request, provide to the Sponsor, monitor or FDA investigator the necessary study records for a thorough review of the study's progress. These records include, but are not limited to, study-specific data forms and original documents and records such as clinic charts, subject informed consent forms, and treatment reports.

All study-specific data forms and other documentation related to the study will be reviewed upon receipt, and the site will be promptly notified of any deficiencies.

## 12.5 FREQUENCY OF MONITORING VISITS

The frequency of monitoring visits will be determined on the basis of several factors, including:

- Duration of the study;
- Number of outstanding issues from previous visits;
- Number of subjects enrolled;
- Number of investigators/sites; and
- Complexity of the study.

Each site will undergo a monitoring visit in compliance with the monitoring plan.

CONFIDENTIAL – PROPRIETARY INFORMATION

## 12.6 STUDY CLOSURE

All routine monitoring functions must be performed prior to the study closure visit; the study closure visit may be combined with a monitoring visit. The following tasks should be completed at the last visit by the monitor:

- Ensure that all forms and images have been sent to the Sponsor;
- Ensure that the Ulthera® System, study transducers, photographic equipment, and any other study supplies or equipment provided to the study site for study use have been returned to the Sponsor;
- Remind the investigator of the obligation to retain the records; and
- Prepare final monitoring report for Sponsor.

## 12.7 REPORTS OF MONITORING VISITS

Monitoring reports must be completed for all visits. Reports must include the following information:

- Date of the visit;
- List of study site personnel present; and
- A summary of the findings, problems, and actions taken to correct any deficiencies;
- A follow-up communication to the Principal investigator and study site outlining the findings, problems, and actions taken to correct any deficiencies.

## 12.8 ADDITIONAL AUDITING

Regulatory authorities worldwide may also audit the investigator during or after the study. The investigator should contact the Sponsor immediately if this occurs, and must fully cooperate with the audits conducted at a reasonable time in a reasonable manner.

## 13. CONFIDENTIALITY

All information generated in this study must be considered highly confidential and must not be disclosed to any persons not directly concerned with the study without written prior permission from the Sponsor. Authorized regulatory officials and Sponsor personnel (or their representatives) will be allowed full access to inspect and copy the records. All investigational devices, subject bodily fluids, and/or other materials collected should be used solely in accordance with this protocol, unless otherwise agreed to in writing by the Sponsor.

Subject names and identifiers will be coded for privacy and subjects will be identified only by unique subject numbers on study-specific data forms. If necessary, their full names may be made known to a regulatory agency or other authorized officials.

## 14. AMENDMENT POLICY

CONFIDENTIAL – PROPRIETARY INFORMATION

The investigator will not make any changes to this protocol without prior written consent from the Sponsor and subsequent approval by the IRB, except if the deviation from the protocol is necessary to protect the life and physical well-being of a subject in an emergency. Such protocol deviations must be reported to the Sponsor and the reviewing IRB as soon as possible, but no later than five working days after the emergency occurred.

Any permanent change to the protocol, whether it is an overall change or a change for specific study center(s), must be handled as a protocol amendment. Any amendment to the protocol that appears indicated as the study progresses will be fully discussed by the investigator(s) and the Sponsor. If agreement is reached regarding the need for an amendment, the Sponsor will write it. The written amendment must be submitted to the chairman of the IRB identified with this responsibility. Except for “administrative amendments”, investigators must await IRB approval of protocol amendments before implementing the change(s). Administrative amendments are defined to have no effect on the validity of the data or information resulting from the completion of the approved protocol, or the relationship of likely patient risk to benefit relied upon to approve the protocol; the scientific soundness of the investigational plan or protocol; and the right, safety or welfare of the human subjects involved in the investigation.

When, in judgment of the chairman of the IRB, the investigators and/or the Sponsor, the amendment to the protocol substantially alters the study design and/or increases the potential risk to the subject, the currently approved written Informed Consent Form will require similar modification. In such cases, repeat informed consent will be obtained from subjects enrolled in the study before continued participation.

## 15. STUDY INVESTIGATORS

All investigators will be experienced with the cosmetic treatments using a variety of accepted clinical modalities.

## **1. INTRODUCTION**

This Statistical Analysis Plan (SAP) is based on the study Protocol Amendment 1 Final v4.0 dated January 26, 2018.

This document provides additional details concerning the statistical analyses outlined in the protocol and reflects any changes to the protocol from any amendments. This plan will not repeat all the definitions given in the protocol but will provide further details of the summaries and analyses planned therein.

The analysis described in this document is only a part of the efficacy analysis outlined in the study protocol to assess the improvement in overall lifting and tightening of skin as determined by a masked, qualitative assessment of photographs at 90 days post-treatment compared to baseline. The analyses for all the other endpoints will be included in a separate statistical analysis plan.

## **2. OBJECTIVE**

The objective is to assess improvement in overall lifting and tightening of skin as determined by a masked, qualitative assessment of photographs at 90 days post-treatment compared to baseline using photographs taken with Mirror Photofile software and a Vectra 3D digital imaging system in each of the treatment groups in Chinese subjects.

## **3. STUDY DESIGN**

This study is an open-label, non-randomized clinical study to be conducted at up to seven clinical sites. Approximately 60 subjects (20 subjects per treatment group) who meet the eligibility criteria will be enrolled and treated with the Ulthera® System. Enrollment eligibility will be determined by the physician and trained assessors' review and approval of screening images, and by the physician's review of inclusion and exclusion criteria.

Eligible subjects enrolled in the study will be treated using the Ulthera® System by the study investigator and/or trained clinician. Standardized images will be taken at screening, baseline (prior to treatment) and following treatment (30 to 60 minutes post-treatment) and at the 90-day post treatment visit using Mirror Photofile software and a Vectra 3D digital imaging system.

Qualitative masked assessment will be conducted following the procedure outlined below:

Ulthera will provide each blinded assessor with identical sets of photos to be assessed: pre-treatment and Day 90 post-treatment photos. The pre/post treatment photos should be consistent in lighting, subject positioning and focus. Each photo's visit interval, i.e., pre and post treatment, will not be marked and randomly assigned to the left and right photo. Each blinded assessor will compare the left and right photo for improvement in the face and rate independently with no inputs from other assessors.

If the assessor sees a change, the assessor marks “Improvement” and chooses which photo shows the improvement (i.e., Left photo or Right photo). If the assessor sees no change, the assessor marks “No change” and does not choose which photo shows improvement.

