**TABLE 3.1-1 SCHEDULE OF ASSESSMENTS**

Evaluation / Procedure	Screening Visit	Baseline / Treatment Visit	Day 7 ± 3 Follow-up	Day 90 ± 14 Follow-up
Informed Consent	√			
Eligibility Assessment (Inclusion/Exclusion  )	√			
Demographics, Medical History, BMI	√			√ 
Pregnancy Screening	√ 			√
Investigator Skin Examination 	√	√		
Selection/Documentation of Treatment Plan 		√		
Treatment of Lower Face, Submental, and Neck		√		
Subject Assessment of Pain 		√		
Vectra 3D Images		√ 		√ 
Quantitative Submental Lift Measure 		√		√
Masked Qualitative Assessments 		√		√
Patient Satisfaction Questionnaire				√
Aesthetic Improvement (Physician Global Aesthetics Improvement Scale - PGAIS)				√
Aesthetic Improvement (Subject Global Aesthetics Improvement Scale - SGAIS)				√
Adverse Event Assessment		*	*	*

\*Complete AE Form when necessary.

1. Screening Form
2. Baseline Clinical Observations (Pre-Treatment) or Clinical Safety and Adverse Events (Post-Treatment and at Follow-up Intervals).
3. Treatment Parameters System Record
4. Subject Pain Assessment Scale using a validated Numeric Rating Scale. Pain scores should be obtained following each region treated and for each transducer used. Record the average pain score for the entire region treated. Overall pain assessment will be completed following treatment completion.
5. Post-treatment images taken 30-60 minutes following Ultherapy® treatment.
6. Pregnancy:
  - a. If a subject becomes pregnant after the Baseline visit and study treatment has been completed, the subject should continue to be followed.
  - b. If a subject becomes pregnant after the Baseline visit but before any study treatments, the subject should be exited from the study.
7. Baseline and 90 day photos to be used after study completion to complete assessment.
8. Obtain height and weight for BMI
9. Subjects may be asked to return to retake Day 90 image if photography issues are noticed following image assessment by photography consultant.

CONFIDENTIAL – PROPRIETARY INFORMATION

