#### 4.5 SUBJECT TREATMENT GROUP ASSIGNMENT

Subjects are not randomized in this study. All subjects will receive an Ultherapy™ treatment at dual depth using the 4-4.5mm and 7-3.0mm transducers. Treatments will be provided to the lower face, submental (under the chin) and neck area. See Section 5.1 for Study Treatment details. Enrolled subjects will be assigned to one of 3 treatment groups:

Group EL2: Subjects will receive an Ultherapy™ treatment at energy level 2 (EL2).

Group EL3: Subjects will receive an Ultherapy™ treatment at energy level 3 (EL3).

Group EL4: Subjects will receive an Ultherapy™ treatment at energy level 4 (EL4).

Twenty subjects will be enrolled in each group. Enrollment from the original protocol was in the following order: EL3, EL4 and EL2. This amendment (dated 26JAN2018) is to change the order of enrollment. Following amendment approval, approximately 20 patients will be enrolled in EL2, EL3 and EL4 respectively. Enrollment will continue at an energy level until that treatment group is complete.

CONFIDENTIAL – PROPRIETARY INFORMATION

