#### **8. STATISTICAL EVALUATION**

The proportion of responders will be summarized using frequency counts and percentages by treatment groups and overall.

In the qualitative assessment, if the assessor marks “Improvement” and the marked photo is not the Post treatment photo, this will be considered as non-response as well as if the assessor rated “No Change”. If the assessor marks “Improvement” and correctly chooses the Post treatment photo, this will be considered as a response. A responder subject is defined as at least 2 out of 3 assessors

select the correct response (i.e., Day 90 photo is deemed as to show improvement) based on the subject's pre/post-treatment photos.

The above endpoint will be summarized for left and right face region separately and combined. A response on both left and right face region will be considered as a response on the whole face region (combing left and right). In addition, a by-subject by-treatment listing will be provided with all results displayed.

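### SAP section 3 gives the masked assessors identical photo sets and states only left/right randomisation; a separate, shuffled, level-balanced reading list per assessor would be better at almost no cost

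*SAP*

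**What the plan says.** SAP section 3 sets out the reading procedure: "Ulthera will provide each blinded assessor with identical sets of photos to be assessed: pre-treatment and Day 90 post-treatment photos". The visit of each photo "will not be marked and randomly assigned to the left and right photo", and assessors "rate independently with no inputs from other assessors". The rating is not a forced choice: where no difference is seen, "the assessor marks “No change” and does not choose which photo shows improvement".

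SAP section 8 turns three votes into one result: "A responder subject is defined as at least 2 out of 3 assessors" choosing the Day 90 photo. For the combined result, "A response on both left and right face region will be considered as a response on the whole face region". SAP Tables 1.1 and 1.2 set the rates for the three energy levels side by side.

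Protocol 4.5 has no random allocation and fills the groups in turn: "Enrollment will continue at an energy level until that treatment group is complete". The order was EL3, EL4, EL2 in the original protocol and is EL2, EL3, EL4 after the amendment. Footnote 7 of protocol Table 3.1-1 puts the reading at the end: "Baseline and 90 day photos to be used after study completion to complete assessment". Protocol 5.3 refers to Attachment F for the qualitative method; its text is redacted in the public file.

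The mock rows of SAP Listing 1 bear on layout. For the right region, assessors 1 and 2 choose the left photo (Baseline) and assessor 3 chooses the right photo (Day 90). For the left region, assessors 2 and 3 both choose the left photo (Day 90). This fits one layout shared by all three assessors but does not prove it.

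**The concern.** Two things are left open in the visible text.

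- **Reading order.** No randomised subject order is stated. Subject order largely tracks energy level because groups are filled in turn. If the set were read in enrolment order, any change during the reading in how readily assessors see improvement would be confounded with energy level.
- **Layout.** If the three sets are identical down to left/right placement, a preference for one side that the assessors share acts on all three votes for the same pair. Rating without contact between assessors does not prevent this, and a 2-of-3 rule cannot remove an error that the voters share.

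At stake is the comparison of masked responder rates between energy levels, and the level of those rates. In a non-randomised study, the reading list is one source of between-group difference that the sponsor fully controls.

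**Working it through.** The plan states no power, alpha or expected rate for this endpoint, so there is no figure to reproduce. All marking, habit, detection and drift values below are assumptions; the documents give none.

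**Majority rule.** If each assessor independently picks Day 90 with probability p, the responder probability for one region is f(p) = 3p²(1 − p) + p³.

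**1. Order.** Take 60 subjects, 20 per level, read EL2, EL3, EL4, with equal true effect. Let p move linearly from p₀ to p₁: pᵢ = p₀ + (p₁ − p₀)(i − 1)/59. Average f(pᵢ) in blocks of 20.

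| p, first to last read | EL2 | EL3 | EL4 | EL4 − EL2 |
|---|---|---|---|---|
| 0.60 to 0.70 | 67.1% | 71.8% | 76.3% | 9.2 points |
| 0.55 to 0.75 | 62.2% | 71.8% | 80.6% | 18.4 points |
| 0.20 to 0.30 | 12.0% | 15.6% | 19.6% | 7.6 points |

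With a shuffled order the expected gap is 0 in every row. For scale, near the 68.6% masked rate of the earlier study in protocol 1.6.1, the standard error of a 20 v 20 difference is √(2 × 0.686 × 0.314 / 20) = 14.7 points.

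**2. Shared side habit, no true change.** Let q be the chance that an assessor marks improvement and h the chance that a mark goes to the left photo. With a separate random layout per assessor the false responder rate is f(q/2), whatever h is. With one shared layout it is [f(qh) + f(q(1 − h))]/2. At q = 0.5, f(0.25) = 15.6% with separate layouts, and:

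| h | Day 90 on left, f(qh) | Day 90 on right, f(q(1 − h)) | Shared layout |
|---|---|---|---|
| 0.7 | f(0.35) = 28.2% | f(0.15) = 6.1% | 17.1% |
| 0.8 | f(0.40) = 35.2% | f(0.10) = 2.8% | 19.0% |
| 0.9 | f(0.45) = 42.5% | f(0.05) = 0.7% | 21.6% |

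At q = 0.7 the separate rate is 28.2%; sharing gives 29.9% (h = 0.7) or 35.2% (h = 0.9). At q = 1 the rate is 50% for every h, because f(h) + f(1 − h) = 1.

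**3. Shared side habit with some true detection.** Suppose a share s = 0.5 of reads truly detect lift and the rest follow q = 0.8, h = 0.9. Separate layouts: f(0.5 + 0.5 × 0.4) = f(0.70) = 78.4%. Shared: [f(0.86) + f(0.54)]/2 = (94.7% + 56.0%)/2 = 75.3%. The shift is small and here runs the other way.

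**4. Chance imbalance in placement.** Under a shared layout with simple random placement, imbalance adds to the difference between two levels an SD of [f(qh) − f(q(1 − h))] × √(2 × 0.25/20). At q = 0.5 this is 0.221 × 0.158 = 3.5 points (h = 0.7) or 0.418 × 0.158 = 6.6 points (h = 0.9). A split of 14:6 or worse in a level of 20 has probability 11.5%. At h = 0.8 a 14:6 split moves that level to 0.7 × 35.2% + 0.3 × 2.8% = 25.5%, or to 12.5% if reversed.

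**5. Whole face (both regions needed).** At q = 0.5, h = 0.9, treating regions as independent given layout: 0.156² = 2.4% with separate layouts; 0.216² = 4.7% if shared by assessors but drawn per region; (0.425² + 0.007²)/2 = 9.0% if one draw serves both regions. The Listing 1 mock shows different layouts for the two regions, so the last case is the least likely.

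**The case against.** The case for leaving the text alone is substantial.

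- Attachment F is redacted and may already set order and layout. Silence in the SAP is not evidence that no rule exists. This stands.
- Identical sets may mean only that every assessor rates the same photos. One mock subject in an output shell cannot settle that. This stands.
- A reader might infer that photos will be read EL2, EL3, EL4, since Listing 1 is arranged by treatment. The documents do not support this. Listing 1 is a results shell; its mock subject number starts with the site, up to seven sites take part, and any subjects enrolled under the EL3-first order would weaken the link. Reading after study completion also lets all levels be mixed.
- A reader might infer that a side habit favours one energy level. It does not in expectation, because placement is randomised.
- A reader might call this the trial's only masked endpoint. That cannot be verified, because the quantitative method in Attachment A is redacted too.
- Visits are unmarked, sides are randomised and ratings are independent. Listing 1 lets the layout be recovered wherever improvement is marked, so a side-preference check is mostly possible already. It is not possible for votes of no change, such as assessor 1's left-region vote in the mock.

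These points limit the size of the concern. They do not supply the missing statement, and the SAP does set out its own reading procedure.

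**Conclusion.** The point holds as a minor, essentially free improvement. The visible SAP states one randomisation, left/right placement, and leaves reading order and per-assessor layout open.

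The order effect is conditional on two things that no document states: reading in enrolment order, and drift. Given both, a modest drift (0.60 to 0.70) produces a gradient of about 9 points with no difference in lift. That is below the 15-point standard error of a 20 v 20 difference, but it is systematic, so a confidence interval would not reveal it.

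The layout effect is conditional on a shared layout and a shared habit. At 50% marking and no true change it adds about 1.5 points (70:30) to 6 points (90:10) to the false responder rate. It adds nothing if every pair is marked, and can reverse when lift is truly detected. Between levels it adds noise rather than bias.

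The documents do not support a claim that the energy-level comparison is biased. The endpoint is secondary (protocol 5.3.2) and descriptive, and no alpha or power depends on it.

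**What to change.** In SAP section 3, replace the identical sets with the same photo pairs presented to each assessor in a separate computer-generated list. Each list should:

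- shuffle the pairs across the three energy levels;
- put Day 90 on the left for half of the pairs within each energy level (or as near as an odd count allows), drawn separately for each assessor and each face region.

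Add the layout per assessor to Listing 1, so that it is also known for votes of no change. If Attachment F already sets these rules, align SAP section 3 with it.

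The cost is three generated lists instead of one and extra columns in Listing 1. No extra reader, photo or visit is needed. Because reading takes place after study completion, all pairs can be available for shuffling.

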#### **4. TREATMENT ASSIGNMENT**

Subjects are not randomized in this study. All subjects will receive an Ultherapy™ treatment at dual depth using the 4-4.5mm and 7-3.0mm transducers. Treatments will be provided to the lower face, submental (under the chin) and neck area. Enrolled subjects will be assigned to one of 3 treatment groups:

Group EL2: Subjects will receive an Ultherapy™ treatment at energy level 2 (EL2).

Group EL3: Subjects will receive an Ultherapy™ treatment at energy level 3 (EL3).

Group EL4: Subjects will receive an Ultherapy™ treatment at energy level 4 (EL4).

#### **5. HARDWARE AND SOFTWARE**

Statistical analysis will be performed following [REDACTED] standard operating procedures and on the [REDACTED] computer network. All statistical analysis will be performed using SAS Version 9.3 or higher with program code prepared specifically for the project by qualified [REDACTED] statisticians and SAS programmers.

#### **6. ANALYSIS POPULATION**

The analysis specified in this document will be based on all subjects enrolled in the study and have both baseline and Day 90 photos available.

#### **7. HANDLING OF MISSING DATA**

No imputation will be performed for missing data.

#### **8. STATISTICAL EVALUATION**

The proportion of responders will be summarized using frequency counts and percentages by treatment groups and overall.

In the qualitative assessment, if the assessor marks “Improvement” and the marked photo is not the Post treatment photo, this will be considered as non-response as well as if the assessor rated “No Change”. If the assessor marks “Improvement” and correctly chooses the Post treatment photo, this will be considered as a response. A responder subject is defined as at least 2 out of 3 assessors

select the correct response (i.e., Day 90 photo is deemed as to show improvement) based on the subject's pre/post-treatment photos.

The above endpoint will be summarized for left and right face region separately and combined. A response on both left and right face region will be considered as a response on the whole face region (combing left and right). In addition, a by-subject by-treatment listing will be provided with all results displayed.

